9.4.2.2 Supportive analyses for primary efficacy

The supportive analyses for the primary analysis results will be performed in two ways:

1. Performing the primary analysis (the LWYY model) and the component analyses (the joint frailty model) on the PPS;
2. Evaluating the impact of the informative censoring of CV death on the estimate of the relative rate reduction through performing additional analyses including:
 - a. Checking of existence of any non-negligible imbalance in CV mortality between treatment groups through analysis for CV mortality alone; pooling PARADIGM-HF (CLCZ696B2314) and this study to assess any adverse signal on CV mortality, if it deems necessary;
 - b. Providing a series of sensitivity analyses to investigate the robustness and consistency of the primary efficacy results:
 - Analysis using the WLW method (Wei et al 1989, Li and Lagakos 1997) on time to first (the conventional time-to-first event analysis) and time to 2nd, 3rd, 4th, 5th, and 6th composite events; an average effect (stratified by event number) will be provided for each of those analyses. This analysis will partially evaluate the robustness of the overall estimate of effect size against the impact from an (expected) small subgroup of patients with higher number of hospitalizations for HF. If the patient's first event is a CV death, then his 2nd, 3rd, ..., Kth event will be counted as CV death as well. This analysis avoids informative censoring by counting CV death repeatedly as event. It is acknowledged that some of the analyses, time-to-1st event, for example, may not be powered;
 - Analysis using a negative binomial regression model (McCullagh and Nelder 1989) on total number of primary composite endpoints with an offset of

logarithm of time from randomization to censoring or death. The common rate ratio of composite events will be provided.

- Analysis using a multi-state model (Castaneda and Gerritse 2010) to assess the hazard ratios of transition intensities between different states defined by hospitalization status and CV death.

9.4.2.3 Secondary analysis

9.4.2.3.1 Analysis methods

The four secondary hypotheses to be tested are:

- Comparison of change from baseline in KCCQ clinical summary score at Month 8 (denoted as H_{210} , the parameter is the mean change from randomized treatment epoch baseline to Month 8 in KCCQ clinical summary score);
- Comparison of change from baseline to Month 8 NYHA class (denoted as H_{220} , the parameter is the category change from baseline to Month 8 in NYHA class);
- Time from randomization to first occurrence of composite renal endpoint of renal death, ESRD, or $\geq 50\%$ decline in eGFR relative to baseline (denoted as H_{230} , the parameter is the hazard ratio for composite renal endpoints);
- All-cause mortality (denoted as H_{240} , the parameter is the hazard ratio for all-cause death).

Changes from baseline in KCCQ clinical summary score at Month 8 will be analyzed based on a repeated measures ANCOVA model in which treatment, region, visit, and treatment-by-visit interaction will be included as fixed-effect factors and baseline value as a covariate, with a common unstructured covariance matrix among visits for each treatment group. Treatment comparisons and effect size estimates at Month 8 will be provided. The analysis will be performed based on all available data up to Month 8 in the FAS and based on likelihood method with an assumption of missing at random for missing data.

In addition, a responder analysis for KCCQ clinical summary score change from randomized treatment epoch baseline at Month 8 (defined as patients with at least 5 point change (deterioration or improvement) will be performed using a generalized mixed model with treatment, region, visit, and visit-by-treatment as fixed factors and baseline score as covariate, with a common compound symmetry covariance matrix among visits for each treatment group. Treatment comparisons and effect size estimates at Month 8 will be provided. The analysis will be performed based on all available data up to Month 8 in the FAS. The goal of the responder analysis is to assess the clinical relevance of the difference between the two groups in the mean change from randomized treatment epoch baseline.

Change from baseline to Month 8 NYHA class will be analyzed using a repeated measures proportional cumulative odds model. The response variable is the category change from baseline to any given time points up to Month 8 (improved, unchanged, worsened). NYHA class change after patients who have died will be categorized into 'worsened'. The model will include patient as a random effect and the randomized treatment phase baseline NYHA class, region, treatment, visit and treatment-by-visit interaction as fixed effect factors. This model assumes that the treatment effect sizes across measurement categories are the same. Model fittings will be based on likelihood with all available data up to Month 8. As supportive

analysis, the same model will be performed on data with no imputation for missing data in NYHA class change due to death.

Time-to-first occurrence of composite renal endpoint events will be analyzed using the Cox proportional hazard model with treatment as a fixed effect factor, stratified by region. The estimated hazards ratio and the corresponding two-sided 95% confidence interval will be provided.

All-cause mortality will be analyzed using Cox's proportional hazards model with a fixed treatment group factor and stratified by region.

9.4.2.3.2 Multiplicity adjustment

The secondary hypotheses will be tested and statistical inferences will be made only if the primary hypothesis is rejected. The four secondary efficacy hypotheses will be tested for superiority of LCZ696 to valsartan for the FAS. For each secondary variable, the null hypothesis of no treatment difference between LCZ696 and valsartan will be tested against the alternative hypothesis that LCZ696 is more effective than valsartan.

[figure not shown]
The sequentially rejective multiple test procedures (Bretz et al 2009) will be used for testing the hypotheses of the primary endpoint and the first three secondary endpoints as indicated in Figure 9-1, to control the alpha level. The all-cause mortality (H_{240}) will be tested at a full level of alpha, after the rejection of the primary hypothesis, considering as a hard-endpoint.

In Figure 9-1, the fractions marked in the graph denote the weights or proportions of alpha to be added to the alphas in the next nodes according to where the arrows point once the current node of hypothesis is rejected.

- The initial allocation of (local) significance levels are α , 0, 0, and 0 for the comparisons of the primary endpoint and the first three secondary endpoints, respectively.
- The general algorithm for the testing procedure goes as follows: Test the hypotheses H_{10} , H_{210} , H_{220} , and H_{230} each at its local significance level defined above. If a hypothesis can be rejected, reallocate its level to one of the other hypotheses according to a pre-specified rule represented by the weighted graph in Figure 9-1. Update the reallocation weights in the reduced graph (the rejected hypothesis is removed from the graph) and repeat the testing step for the remaining no-rejected hypotheses with the updated local significance levels. This possibly leads to further rejected null hypotheses with associated reallocation of the local significance levels. The procedure is repeated until no further hypothesis can be rejected. The reallocation of the local alpha levels is fully determined by the initial graph given in Figure 9-1 and the update algorithm for this sequentially rejective multiple test procedure (Bretz et al 2009).
 - In the notation of Bretz et al 2009, a weight of ε for an edge indicates an infinitesimally small weight. If a hypothesis (vertex) with such an outgoing edge is rejected and the vertex removed, no significance level is passed on along such an edge as long as there are other outgoing edges with positive weights. If after removal of another vertex only infinitesimal outgoing edges remain, then the algorithm of Bretz et al 2009 turns them into edges with positive weights that sum to 1. In this specific procedure, this implies that no significance level is passed from the secondary null hypotheses for KCCQ (H_{210}) or NYHA class (H_{220}) to the secondary null hypothesis

for composite renal endpoint (H_{230}) until both KCCQ and NYHA class null hypotheses have been rejected. To ensure the sum of weights on all outgoing edges of a vertex is 1 when such edges are present, some edges are given a weight of $1 - \epsilon$.

Figure 9-1 Illustration of weights for alpha relocation in the sequentially rejective multiple test procedure for the secondary hypotheses

The power analyses for each hypothesis in [Figure 9-1](#) are presented in [Section 9.7](#).

For publications the secondary variables may be assessed using a full level of alpha without consideration of multiplicity adjustment.

9.4.2.4 Subgroup analyses for primary and secondary objectives

Subgroup analyses will be performed for the primary and secondary endpoints based on the FAS. To explore beneficial effects in subgroups or homogeneity of beneficial effects among subgroups, the estimated effect sizes, their two-sided 95% confidence intervals, and within subgroup p-value and p-value for the test for the treatment-by-subgroup interaction will be provided for each of the subgroups based on the analysis models. The analysis models will include treatment, subgroup, and treatment-by-subgroup as fixed-effect factors, except for NYHA. No adjustment for multiple comparisons will be made. Therefore, p-values from these subgroup analyses have to be interpreted with caution since there is a non-negligible chance of false-positive findings.

- Age group (<65 vs. ≥65 years; <75 vs. ≥75 years)
- Gender (male/female)
- Race
- Region
- Diabetic at baseline (yes/no)
- Baseline SBP (≤median vs. >median)

- Baseline LVEF (\leq median vs. $>$ median)
- Baseline NT-proBNP (\leq median vs. $>$ median)
- Baseline eGFR (<60 vs ≥ 60 mL/min/1.73 m²)
- AF at baseline (yes/no)
- Use of MRAs at baseline (yes/no)
- ACEI intolerant patients (yes/no)

9.4.3 Handling of missing values/censoring/discontinuations

The primary efficacy variable, the recurrent extended composite events and time to new onset of AF variables are related to the number of events or time to event occurred within a certain time window. The censoring will be the major source of missing data. This type of missing data will be handled by assuming some dependence structures between the censoring mechanism and the event generating mechanism. The dependence structures will be pre-specified in the analysis plan. A variable is considered to be censored at each analysis time point if at least one of the following applies at or prior to the analysis time point:

- Withdrawal of informed consent,
- Lost to follow-up, or
- Death

The censoring date will be defined as the following (whichever occurs first):

- Date when the patient withdrew informed consent
- Date of the patient's last visit before analysis cut-off date
- Date of death

For the analysis of KCCQ clinical summary score, if a patient dies, a worst score (score of 0) will be imputed for the clinical summary score at all subsequent scheduled visits after the date of death where the clinical summary score would have been assessed.

For the analysis of NYHA, the analysis will be based on the likelihood approach. The missing at random (MAR) for missing data is assumed. An unbiased analysis will be produced under MAR.

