5.5.9 Discontinuation of study treatment

Patients may voluntarily discontinue study treatment for any reason at any time. However; study treatment discontinuation does not constitute withdrawal from the study, does not constitute withdrawal of consent and should not lead to the patient being withdrawn from the entire study. Patients who have discontinued study drug are expected, and should be

encouraged to, attend all the protocol specified study visits and perform all measurements as stipulated in the visit schedule (Table 6-1) and remain in follow up for the duration of the trial. If they fail to return for these assessments for unknown reasons, every effort should be made to contact them as specified in Section 5.5.11. The investigator must also contact the IRT to register the patient's interruption from study treatment and record it on the drug administration form CRF.

If the patient does not attend the study visits, follow-up should continue according to the specified schedule by telephone to determine if any AEs/endpoints pre-specified in the protocol have occurred, except in the case that the patient **specifically** refuses such follow-up and withdraws his/her consent.

The emergence of the following circumstances will require permanent study drug discontinuation:

- Withdrawal of informed consent
- Investigator thinks that continuation would be detrimental to the patient's well-being
- Suspected occurrence of angioedema. A patient with any signs or symptoms of clinically significant angioedema should be thoroughly evaluated by the investigator

The emergence of the following circumstances will require temporary or permanent discontinuation (study drug may be restarted once these circumstances no longer exist):

- Use of an open label ACEI, ARB or renin inhibitor
- Pregnancy and post-pregnancy during lactation period (Section 7.5)

Study drug may be discontinued at the investigator's discretion if any of the following occurs:

- Any severe suspected drug-related AE
- Any other protocol deviation that results in a significant risk to the patient's safety

The appropriate personnel from the site and Novartis will assess whether study drug should be permanently discontinued for any patient whose treatment code has been broken inadvertently for any reason.

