8.6 Source documentation verification

Novartis will select patients based on pre-defined criteria (e.g., enrollment based on elevated NT-proBNP alone or based on prior hospitalization for heart failure) for collection of select source documentation of medical history records for full medical review of adherence to the inclusion/exclusion criteria as needed to ensure the intended per protocol target patients are enrolled. Sites will be instructed to remove all personal identifiers linking the source documents to the patients prior to submission to a third party vendor via electronic email or fax. The third party vendor will then ensure anonymity of the documents, compile the medical history packets, translate the documents into English (if applicable), and forward them to Novartis for medical review. Only the patient's study identification number will be used to ensure patient's identity and confidentiality are preserved. The review will be conducted centrally by the global study clinical team and will focus on enrolled patients. The aim of this central medical review is to assess compliance with the protocol and provide additional training to the investigator sites if needed.

9 Data analysis

This section describes a preliminary approach to data analysis.

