The primary hypothesis will be tested at a one-sided significance level of 0.02499 adjusted for interim analysis. The rate ratio and its 95% confidence interval will be estimated from the above proportional rates model through maximization of a partial likelihood score function. The resulting estimate of $\exp(\beta_0)$ is identical to the one described by Anderson and Gill (Anderson and Gill 1982), but unlike Anderson-Gill, a robust variance estimator (sandwich estimator) is used to account for the dependency of within subject events. Note that having CV death is not considered as a censoring variable, but as a primary endpoint event and a conditional factor in this analysis. Time to non-CV death will be considered as a censoring variable. Any censoring due to non-CV death is assumed to be non-dependent in the analysis.

The above presented analysis method based on LWYY provides a treatment comparison based on primary endpoint rate ratio conditional on not having died from a CV reason. A marginal interpretation of the estimates requires that any censoring of the primary composite events will be non-informative and may be challenging if there is an imbalance in CV mortality.

As a part of the primary analysis, the two components in the composite endpoint (total HF hospitalizations and CV mortality) will be analyzed separately to quantify the respective treatment effects and check the consistency between the composite and the components.

For the analysis of total HF hospitalizations component, occurrence of CV death can be regarded as semi-competing risk (informative censoring) and may introduce a bias in the treatment effect estimate for HF hospitalizations (dilution of effect size if the drug has a positive effect on both components). In order to address this concern and to account for the correlation between the two components, the joint modeling (frailty model) approach (Cowling et al 2006) will be used for the component analyses. The joint model is specified as follows.

$$\begin{aligned}\lambda_{ij}^H(t) &= Y_{ij}(t)\lambda_0^H \exp(\beta_0 x_{ij})v_{ij} \\ \lambda_{ij}^T(t) &= Y_{ij}(t)\lambda_0^T \exp(\gamma_0 x_{ij})v_{ij}^\alpha \\ v_{ij} &\sim f(\cdot)\end{aligned}$$

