- For all-cause death, the censoring will occur at minimum (date of withdrawal of consent, last known alive date, analysis cutoff date)
- For CV death, the censoring will occur at minimum (date of withdrawal of consent, last known alive date, analysis cutoff date, date when patient died for non-CV causes)
- For a non-mortality and non-composite endpoint, the censoring will occur at minimum (date of withdrawal of consent, date of lost to follow-up, analysis cutoff date, date when patient died)
- For a composite endpoint, the censoring will occur at the earliest censoring date among the components.

In some additional analyses, one may be interested in all events occurring before major protocol deviations. In such cases, the events occurred after having major protocol deviations need to be censored. The censoring variables are:

- Minimum (the censoring time defined for the primary, secondary, exploratory analyses, date of the first major protocol deviation).

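### Protocol 9.4.3 censors the primary variable at the earliest of consent withdrawal, last visit or death of any cause; this contradicts Protocol 9.4.2.1 and the SAP and needs reconciling

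*Protocol*

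**What the plan says.** **Protocol 9.4.3.** The scope is explicit: "The primary efficacy variable, the recurrent extended composite events and time to new onset of AF variables". Three reasons for censoring are listed: consent withdrawal, loss to follow-up, and death with no cause given. The date rule then reads "The censoring date will be defined as the following (whichever occurs first", followed by three dates: consent withdrawal, the patient's "last visit before analysis cut-off date", and death.

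**Protocol 9.4.2.1.** In the primary analysis, "having CV death is not considered as a censoring variable, but as a primary endpoint event". The only death that censors is non-CV: "Time to non-CV death will be considered as a censoring variable".

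**SAP 9.1 and 9.3.1.** All adjudication-confirmed primary events from randomization to the analysis cut-off are included. The note to the SAS code in SAP 9.3.1.1 gives a CV death status 1, meaning an event.

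**SAP 9.2.** "For CV death, the censoring will occur at minimum (date of withdrawal of consent, last known alive date, analysis cutoff date", with the date of non-CV death as the fourth term. For non-mortality, non-composite endpoints the dates are consent withdrawal, loss to follow-up, cut-off and death of any cause. A composite takes the earliest date among its components.

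**Follow-up after treatment or visits stop.** Protocol 5.5.9 says that when patients no longer attend, "follow-up should continue according to the specified schedule by telephone". Protocol section 6 also asks sites to obtain endpoint status from an informant if necessary.

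**The concern.** The primary endpoint has two end-of-follow-up rules that cannot both be applied. One puts a last-visit limit and all-cause death into a minimum. The other counts CV death as an event and runs to the cut-off.

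Take a patient seen at month 12 who dies a CV death at month 14. Under the words of 9.4.3 the earliest listed date is month 12, and the death falls outside follow-up. Under 9.4.2.1 and the SAP it is a primary event at month 14.

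Part of the conflict does not depend on how CV death is read. After week 48, contacts are 12 weeks apart (Protocol section 6). SAP section 4 allows the final visit to fall just after the cut-off. A survivor hospitalized for HF between the last pre-cut-off visit and the cut-off counts under SAP 9.1 and 9.3.1, but is past the 9.4.3 date.

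At stake is which events make up the primary endpoint of a registration trial. CV death is also the component for which the design expects the smaller effect, so a rule that removes it would move the estimate in favor of LCZ696.

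**Working it through.** **1. The rules side by side (primary endpoint)**

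| | Protocol 9.4.3 | Protocol 9.4.2.1 | SAP 9.1, 9.2, 9.3.1 |
|---|---|---|---|
| CV death | in the censoring list, cause not separated | event | event (status 1) |
| Non-CV death | censors | censors | censors |
| Last visit before cut-off | censors | not mentioned | not used |
| Last known alive or lost-to-follow-up date | no date of its own | not mentioned | censors |
| Analysis cut-off | only through the last visit | not mentioned | censors |

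**2. Size of the CV-death component**

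Inputs are 4600 patients, 1847 target events, and CV mortality of 0.036 per year before and 0.040 after up-rating (Protocol 9.7.1). Average follow-up is 3.375 years (Protocol 9.7.3.4), which agrees with the design: 26/12 + (29/12)/2 = 3.375.

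Expected CV deaths = 4600 × (1 − exp(−r × 3.375)):
- r = 0.036: 526, or 526/1847 = 28.5%
- r = 0.040: 581, or 581/1847 = 31.5%

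This is how many CV deaths the design expects. It is not an estimate of events that will be lost.

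**3. Reproducing the design figure**

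The model is the plan's shared gamma frailty with shape θ = 0.193, Poisson HF hospitalizations and exponential CV death. Allocation is 1:1, enrollment uniform over 29 months, minimum follow-up 26 months, RR 0.70 for HF hospitalization and HR 0.90 for CV death. The analysis is LWYY with sandwich variance at one-sided 0.025, without region strata.

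Under this frailty, the annualized rate over T years is (θ/T) × ln(1 + λT/θ). The plan does not state T for its 0.09 (first event) and 0.04 (CV death) rates, so I solved for λ at two values:
- T = 3.375: total λ = 0.2187, CV death 0.0579, HF hospitalization 0.1608 per year
- T = 3.0: total λ = 0.1963, CV death 0.0555, HF hospitalization 0.1408 per year

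Power is 0.957 and 0.941 (plan: 0.95). The rate ratio is 0.778 and 0.780 (plan: 0.778). Total events are 1935 and 1765, which bracket 1847. The power and rate ratio are reproduced; the event count is bracketed but not pinned.

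**4. The literal 9.4.3 rule in the same model**

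Patients who die a CV death before the cut-off are censored at the preceding scheduled visit, telephone visits included. Survivors are followed to the cut-off.

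| Calibration | Events, CV death counted | of which CV deaths | Events, literal 9.4.3 | Lost | Rate ratio | Power |
|---|---|---|---|---|---|---|
| T = 3.375 | 1935 | 556 | 1338 | 597 (31%) | 0.778 → 0.726 | 0.957 → 0.972 |
| T = 3.0 | 1765 | 540 | 1190 | 575 (33%) | 0.780 → 0.723 | 0.941 → 0.962 |
| daily rates × 1.08 | 1636 | 528 | 1077 | 559 (34%) | 0.779 → 0.719 | 0.945 → 0.966 |

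HF hospitalizations lost are 597 − 556 = 41 and 575 − 540 = 35 in the first two rows. Ending survivors at their last scheduled visit as well removes about 30 more events (1338 to 1305, and 1190 to 1160).

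Power does not fall. What changes is the endpoint: all CV deaths go, and the rate ratio moves toward the 0.70 assumed for HF hospitalization.

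**The case against.** A reader might infer that 9.4.3 cuts off every CV death because the last visit always precedes death. The documents do not support this.

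- A death can fall on a visit day, and SAP section 4 sets the final visit of a patient who died to the day of death.
- 9.4.3 lists death as a date of its own. That item would hardly ever operate if the last visit came first for everyone. The natural reading is that the last visit serves patients not known to have died.
- Protocol 9.4.2.1 states that CV death is an event. Losing every CV death requires 9.4.3 to override it.
- Protocol section 9 opens with "This section describes a preliminary approach to data analysis". The SAP counts confirmed events to the cut-off and codes CV death as an event.
- Telephone and informant information is not shown to be lost. Protocol section 6 treats telephone contacts as visits, and SAP section 4 dates the final visit of a patient reached only by telephone or indirectly to the day the records are taken.

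All of this stands, and it removes any claim of a projected loss.

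Two further points bear on the remedy. Under SAP 9.2 the last known alive date also sits inside a minimum and cannot be later than death, so the same literal reading would remove CV deaths there too. And the SAP's CV-death rule is not its rule for the primary endpoint: the composite takes the earliest component date, so death of any cause enters through HF hospitalization. Copying SAP 9.2 into the protocol would therefore not cure the wording.

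The contradiction itself is not removed. The preliminary label does not say which rule governs. 9.4.3 leaves to the analysis plan only the dependence between censoring and events, and defines the date itself. SAP section 1 refers back to the protocol's data analysis section, and numbers it 10, which in this protocol is ethics.

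**Conclusion.** The point holds as an inconsistency. For the primary variable, Protocol 9.4.3 conflicts with Protocol 9.4.2.1 on CV death, and with SAP 9.1, 9.2 and 9.3.1 on the last-visit limit.

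If 9.4.3 were applied to the letter, about 31–33% of events would go (34% if the daily rates are simply multiplied by 1.08). The rate ratio would move from about 0.78 to about 0.725, with power at 0.96–0.97. The harm would be a changed endpoint, in effect HF hospitalization only, and not lost power. An analysis that follows the SAP does not lose these events.

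The figures assume the plan's frailty model and effect sizes, scheduled visits attended on time, survivors followed to the cut-off, and a horizon of 3.0 to 3.375 years for the annualized rates. The conflict in the wording needs none of these assumptions.

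**What to change.** In Protocol 9.4.3:

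1. State that a CV death on or before the analysis cut-off is a primary event on its own date. It ends the at-risk period and is never a censoring date.
2. For patients without CV death, censor at the earliest of consent withdrawal, non-CV death, the last contact at which endpoint status was obtained, and the analysis cut-off. Telephone and informant contacts count, and this contact date serves for patients lost to follow-up.
3. Delete the item "last visit before analysis cut-off date".

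In SAP 9.2, add the same clarification to the composite rule, so that neither the last known alive date nor the earliest component date can be read as censoring a CV death.

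The cost is a few words in each document, or a note to file. No new data are needed, and the sample size, power and model are unaffected.
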